## Title page

# **Whole-body photobiomodulation for muscle performance enhancement, attenuation of muscular damage and delayed onset muscle soreness in professional soccer athletes – randomized sham-controlled trial**

## Abstract

**Context:** Photobiomodulation (PBM) has recently been applied in sports to enhance physical performance and mitigate muscle damage and delayed-onset muscle soreness (DOMS). These effects may be particularly relevant when PBM is delivered to large body areas through whole-body irradiation. **Objective:** To evaluate the effects of whole-body PBM on muscle damage, DOMS, and muscle performance in professional soccer athletes undergoing a muscle damage induction protocol. **Methods:** A randomized, double-blind, sham-controlled trial was conducted with 30 professional soccer players from a Brazilian team. Participants were randomly allocated into three groups ( $n = 10$  each): (a) PBM-post, (b) PBM-pre, and (c) PBM-sham. Outcomes included serum creatine kinase (CK) levels, DOMS (numeric rating scale [NRS] and pain mapping [mapDOMS]), muscle performance (squat jump [SJ] and countermovement jump [CMJ]), and isometric dynamometry of the knee extensors. All groups received PBM irradiation (active or sham), followed by the muscle damage induction protocol, and subsequent PBM irradiation (active or sham). Assessments were performed at baseline, 24 h, 48 h, and 72 h post-induction. **Results:** CK levels significantly increased ( $p < 0.05$ ) at 24–72 h in the sham group and at 24–48 h in the PBM-post group. In contrast, the PBM-pre group showed no significant increase ( $p > 0.05$ ) across 24–72 h. For DOMS (NRS), the sham group

reported significant increases ( $p < 0.05$ ) from 24–72 h, the PBM-pre group only at 24 h, and the PBM-post group at no time point. DOMS assessed by mapDOMS showed no significant changes ( $p > 0.05$ ) across groups or time points. No significant differences ( $p > 0.05$ ) were observed in muscle performance outcomes among groups. **Conclusion:** Pre-exercise PBM provided protective effects against muscle damage (lower CK) and reduced DOMS at 48–72 h, while post-exercise PBM reduced DOMS consistently at all time points (24–72 h). Neither pre- nor post-exercise PBM improved or worsened muscle performance.

**Keywords:** CK; DOMS; light-emitting diode; low-level laser therapy; recovery

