### **b) Measurement of Blood Levels of Creatine Phosphokinase (CK):**

The analyses were carried out by a clinical analysis laboratory (LabCenter Diagnostics Integrates, Itu, SP, Brazil) in a blinded manner, meaning they were unaware of the therapies applied to each participant. Briefly, the athletes rested for about 10 minutes in a seated position before blood collection. The material was labeled, and the forearm was aseptically cleaned with 70% alcohol. Using a 25x8 multiple collection needle, a vein in the antecubital fossa was punctured, and a 5 ml vacuum collection gel tube was inserted for CK analysis. Subsequently, the measurement was performed on a Roche Hitachi 917 biochemical analyzer using enzymatic methodology. A biomedical professional from the laboratory, not involved in the study, assessed the results in U/L. This analysis was conducted at baseline (T1), i.e., before the muscle damage induction protocol, and at 24h, 48h, and 72h after (T3).

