### STATISTICAL ANALYSIS PLAN (SUMMARY)

Primary endpoint: Serum CK levels (U/L) over time.

Secondary endpoints: DOMS (NRS and mapDOMS), SJ and CMJ jump heights (cm), and isometric knee extensor force (kgf).

Statistical tests:

- Normality (Shapiro–Wilk) and homogeneity (Levene).
- Two-way repeated measures ANOVA with Tukey post hoc (parametric).
- Friedman and Kruskal–Wallis (nonparametric when assumptions not met).
- Significance level:  $\alpha = 0.05$ .

Software: IBM SPSS Statistics v20.0.

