## Data Analysis

Data analysis was conducted by a researcher blinded to participant group allocation. The primary outcome of the study was considered the muscle damage measured by CK levels.

The data were descriptively analyzed using mean and standard deviation. The independent variables were the experimental conditions (Sham, PBM-pre, and PBM-post) and assessment times pre, 24h, 48h, 72h after the muscle damage induction protocol. Normality and homoscedasticity assumptions were tested beforehand using the Shapiro-Wilk W Test and Levene test, respectively. The dependent variables included CK, DOMS, height of jumps in Squat Jump (SJ) and Counter Movement Jump (CMJ), and isometric manual dynamometry of the femoral quadriceps (kgf).

Two-way repeated measures analysis of variance (ANOVA) was conducted (considering pre, 24h, 48h, and 72h after the muscle damage induction protocol) followed by Tukey's post hoc test when the data showed normal distribution and variance homogeneity. In cases where the data did not present normal distribution, a logarithmic transformation (log10) was adopted, and normality and variance homogeneity were verified again for parametric tests. If the data did not meet the assumptions of normality and variance homogeneity, non-parametric tests such as Friedman's ANOVA (intragroup analyses) and Kruskal-Wallis (intergroup analyses) were employed. The significance level was set at 5%. Statistical analysis was performed using a statistical software (SPSS Statistics for Windows version 20.0, IBM, Chicago, IL, United States).

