### Creatine Kinase (CK)

The CK data in U/L did not follow a normal distribution, and a logarithmic transformation ( $\log_{10}$ ) was applied. After the transformation, the data showed a normal distribution and homogeneity of variances for conducting parametric tests. Repeated measures ANOVA revealed a moment interaction ( $F_{2,27} < 0.001$ ) and a moment versus treatment interaction ( $F_{2,27} < 0.001$ ). Tukey's post hoc test identified significant differences as shown in the table below:

[figure not shown]
**Table 5.** Mean values ( $\pm$ standard deviation) of creatine phosphokinase (CK) in U/L for the Sham, PBM-pre, and PBM-post groups at pre, 24h, 48h, and 72h after the muscle damage induction protocol:

| Groups   | CK pre                 | CK 24h                  | CK 48h                  | CK 72h                  |
|----------|------------------------|-------------------------|-------------------------|-------------------------|
| Sham     | 289.2 ( $\pm 209.94$ ) | 661.5 ( $\pm 477.24$ )* | 491.6 ( $\pm 285.44$ )* | 523.2 ( $\pm 343.15$ )* |
| PBM-pre  | 249.2 ( $\pm 112.28$ ) | 372.7 ( $\pm 190.58$ )  | 424.2 ( $\pm 248.90$ )  | 392.6 ( $\pm 215.23$ )  |
| PBM-post | 287.8 ( $\pm 199.09$ ) | 794.5 ( $\pm 763.80$ )* | 631.2 ( $\pm 512.08$ )* | 271.44 ( $\pm 133.27$ ) |

**Abbreviations:** PBM (photobiomodulation); CK (creatine phosphokinase). \* p-value  $< 0.05$  in two-way repeated measures ANOVA followed by Tukey's post hoc analysis.

Compared to the pre-moment of the muscle damage induction protocol, there was a significant increase in CK levels in the Sham group ( $p = 0.001$ ) and PBM-post group ( $p = 0.001$ ) at the moment 24h after, while in the PBM-pre group the increase was not significant ( $p = 0.285$ ). When comparing the pre-moment of the muscle damage induction protocol to 48h after, the Sham group had a significant increase in CK ( $p = 0.028$ ), as well as the PBM-post group ( $p = 0.015$ ), while the PBM-pre group did not show a significant increase ( $p = 0.131$ ). In the

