comparison between the pre-moment of the muscle damage induction protocol and 72h after, only the Sham group had a significant increase in CK ( $p = 0.010$ ), while the PBM-pre and PBM-post groups did not show significant increases ( $p = 0.506$ ;  $p = 1.000$ , respectively). In the comparison between groups for the respective CK assessment moments, there were no significant differences ( $p > 0.05$ ). The graphical representation of these results is in Figure 4.

**Figure 4.** Results for creatine phosphokinase (CK) at the evaluated time points (pre-moment of muscle damage induction protocol, 24h, 48h, and 72h after), and experimental groups (Sham, PBM-pre, PBM-post). Values presented in both log10-transformed and raw formats. Data expressed as mean ( $\pm$  standard error).

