#### Delayed Onset Muscle Soreness (DOMS) measured by the Numeric Rating Scale (NRS).

Repeated measures ANOVA revealed a moment interaction ( $F_{2,27} < 0.001$ ) and a moment versus treatment interaction ( $F_{2,27} = 0.044$ ). Tukey's post hoc analysis identified significant differences as shown in Table 6.

[figure not shown]
**Table 6.** Mean values ( $\pm$  standard deviation) of Delayed Onset Muscle Soreness (DOMS) measured by the Numeric Rating Scale (NRS) for the Sham, PBM-pre, and PBM-post groups at pre, 24h, 48h, and 72h after the muscle damage induction protocol:

| Groups | DOMS (NRS)          | DOMS (NRS)           | DOMS (NRS)           | DOMS (NRS)           |
|--------|---------------------|----------------------|----------------------|----------------------|
|        | pre                 | 24h                  | 48h                  | 72h                  |
| Sham   | 0.60 ( $\pm 1.26$ ) | 5.70 ( $\pm 2.05$ )* | 4.20 ( $\pm 2.39$ )* | 3.20 ( $\pm 2.78$ )* |

|                 |                     |                      |                     |                     |
|-----------------|---------------------|----------------------|---------------------|---------------------|
| PBM-pre  | 1.20 ( $\pm 1.61$ ) | 3.80 ( $\pm 2.74$ )* | 2.80 ( $\pm 1.54$ ) | 1.70 ( $\pm 1.82$ ) |
| PBM-post | 1.30 ( $\pm 2.11$ ) | 3.00 ( $\pm 2.00$ )  | 2.40 ( $\pm 1.83$ ) | 2.10 ( $\pm 1.72$ ) |

**Abbreviations:** PBM (photobiomodulation); DOMS (Delayed Onset Muscle Soreness); NRS (Numeric Rating Scale); \* p-value < 0.05 in two-way repeated measures ANOVA followed by Tukey's post hoc analysis.

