Compared to the pre-moment of the muscle damage induction protocol, there was a significant increase in DOMS measured by the NRS in the Sham group ( $p < 0.001$ ) and PBM-pre group ( $p = 0.027$ ) at the moment 24h after, while the PBM-post group did not show a significant increase ( $p = 0.460$ ). In the comparison between the pre-moment of the muscle damage induction protocol and 48h after, the Sham group had a significant increase in DOMS (NRS) ( $p < 0.001$ ), while the PBM-pre and PBM-post groups did not show significant increases ( $p = 0.555$ ;  $p = 0.933$ , respectively). In the comparison between the pre-moment of the muscle damage induction protocol and 72h after, only the Sham group had a significant increase in DOMS ( $p = 0.027$ ), while the PBM-pre and PBM-post groups did not show significant increases ( $p = 0.999$ ;  $p = 0.993$ , respectively). In the comparison between groups for the respective moments of DOMS (NRS) assessment, there were no significant differences ( $p > 0.05$ ). The graphical representation of these results is in Figure 5.

**Figure 5.** Results for Delayed Onset Muscle Soreness (DOMS), measured by the Numeric Rating Scale (NRS) at the evaluated time points (pre-moment of muscle damage induction protocol, 24h, 48h, and 72h after), and experimental groups (Sham, PBM-pre, PBM-post). Data expressed as mean ( $\pm$  standard error).

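### Arm-specific benefit is concluded without a planned baseline-adjusted PBM-vs-Sham estimate or interval, and with the Tukey family and error term unstated

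*Combined protocol and SAP*

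**What the plan says.** The Statistical Analysis Plan (Summary) gives the parametric analysis as "Two-way repeated measures ANOVA with Tukey post hoc (parametric". The Data Analysis section adds the levels of time: "Two-way repeated measures analysis of variance (ANOVA) was conducted (considering pre, 24h, 48h, and 72h after the muscle damage induction protocol". Baseline is thus an outcome level, not a covariate. Neither section names a PBM-vs-Sham contrast, the set of comparisons that Tukey covers, the error term, or a confidence interval. Planned summaries are means and standard deviations.

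Baseline CK was planned for all athletes: "This analysis was conducted at baseline (T1), i.e., before the muscle damage induction protocol, and at 24h, 48h, and 72h after (T3".

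The Creatine Kinase results report "and a moment versus treatment interaction ( $F_{2,27} < 0.001", and the NRS results report "and a moment versus treatment interaction ( $F_{2,27} = 0.044". Both are printed as F values but read as p-values. Each is followed by p-values for change from baseline within each arm. On the arms themselves the text says only "In the comparison between groups for the respective CK assessment moments, there were no significant differences" for CK and "In the comparison between groups for the respective moments of DOMS (NRS) assessment, there were no significant differences" for NRS, with no estimate, exact p-value or interval. The Abstract nevertheless concludes "Pre-exercise PBM provided protective effects against muscle damage (lower CK) and reduced DOMS" (the latter at 48-72 h), and that post-exercise PBM lowered soreness at all times.

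**The concern.** A significant rise in Sham and a non-significant rise in PBM-pre do not show that the two rises differ. With 10 athletes per arm, the same true rise can easily be significant in one arm and not in another. The interaction test does compare changes between arms, but over three arms and four times it is an omnibus test. The pairwise tests that should locate the effect use levels without baseline and were all reported as null.

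At stake is what the trial may claim on its primary endpoint (CK) and on soreness. The omnibus result stands, but the attribution to a particular arm and time has no between-arm estimate behind it.

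**Working it through.** **1. The plan's own sample size.** Inputs from section 3.7: 3 groups, 4 times, effect size 0.25 (read as Cohen's f), 80% power, alpha 5%. For the group-by-time interaction, lambda = f²·N·m/(1 − rho), with df (3 − 1)(4 − 1) = 6 and (N − 3)·3. With rho = 0.5 and sphericity (both assumed), N = 30 gives power 0.809. With rho 0.3 or 0.7 the required N would be 42 or 21. The stated 30 therefore fits the omnibus interaction, not a pairwise contrast.

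**2. Which Tukey family was used.** Two NRS changes of 2.6 points have reported p = 0.027. Solving for the error variance and predicting the other within-arm p-values:

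| Change | Reported p | 12 cells, 81 df (error 2.636) | 4 times, 81 df (error 4.129) |
|---|---|---|---|
| 1.7 | 0.460 | 0.457 | 0.249 |
| 1.6 | 0.555 | 0.552 | 0.300 |
| 1.1 | 0.933 | 0.932 | 0.622 |
| 0.8 | 0.993 | 0.994 | 0.815 |

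The NRS results fit a family of all 12 arm-by-time cells; for CK this is unconfirmed. The same error applied to Sham vs PBM-post at 24 h (5.7 − 3.0 = 2.7) would give p = 0.018, against the reported absence of differences. With the full between-athlete variance (mean of squared SDs in Table 6, 4.148), 12 cells give p about 0.14 to 0.17. A 3-arm Tukey at 24 h gives 0.035. The reported null thus depends on choices written nowhere.

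**3. What the family costs.** Critical |t| is 2.33 for two Dunnett contrasts (27 df), 2.48 for a 3-arm Tukey (27 df) and 3.37 for 12 cells (81 df). The difference detectable at one time with 80% power is 1.43, 1.50 and 1.89 SD respectively. Baseline-adjusted Dunnett (residual SD √(1 − rho²), 26 df) gives 1.37, 1.24 and 1.02 SD at rho 0.3, 0.5 and 0.7.

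**4. CK, PBM vs Sham.** Table 5 was converted to log10 by lognormal moments. Means over 24, 48 and 72 h:
- Sham: (2.730 + 2.629 + 2.641)/3 = 2.667
- PBM-pre: (2.521 + 2.563 + 2.537)/3 = 2.540
- PBM-post: (2.758 + 2.690 + 2.387)/3 = 2.612

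PBM-pre minus Sham is −0.126 (from unrounded means). Baselines differ by 2.356 − 2.369 = −0.013. At rho = 0.5 the slope is 0.517, so the adjusted difference is −0.126 + 0.517 × 0.013 = −0.119, a ratio of 10^−0.119 = 0.76. Simultaneous 95% intervals run from 0.50-1.15 (rho 0.3) to 0.54-1.08 (rho 0.7), with Dunnett p 0.15 to 0.22. For PBM-post the ratio is 0.88 (0.58-1.33 to 0.62-1.24).

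Per time, at rho 0.5 and before any multiplicity adjustment, PBM-pre/Sham is 0.63 (0.39-1.02), 0.87 (0.55-1.38) and 0.80 (0.50-1.28). PBM-post/Sham is 1.06 (0.57-1.96), 1.15 (0.67-1.95) and 0.55 (0.35-0.87).

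**5. NRS, PBM vs Sham.** Table 6 means over 24-72 h are 4.37 (Sham), 2.77 (PBM-pre) and 2.50 (PBM-post), so the unadjusted differences are −1.60 and −1.87. Baselines are 0.6 and 0.7 points higher in the active arms. Dunnett p after baseline adjustment (26 df):

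| Correlation baseline-later / among later | PBM-pre p | PBM-post p |
|---|---|---|
| 0.3 / 0.3 | 0.016 | 0.005 |
| 0.5 / 0.5 | 0.007 | 0.002 |
| 0.7 / 0.7 | 0.001 | <0.001 |
| 0.2 / 0.52 | 0.06 | 0.03 |
| 0.1 / 0.62 | 0.10 | 0.05 |

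The last two rows keep the average correlation at 0.36, the value implied by step 2 (1 − 2.636/4.148).

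**6. Athletes per cell.** 271.44 × 9 = 2442.96, close to a whole number, 2443 (2443/9 = 271.44). But 271.44 × 10 = 2714.4. The PBM-post 72 h CK mean fits nine whole-number values, not ten.

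**The case against.** The strongest reply is that arms were compared. The interaction tests differences in change, Tukey covers all pairs, and PBM-vs-Sham was tested at each time and reported as null. That stands. A reader might infer that the trial has no between-arm test at all, and the documents do not support that. What is missing is baseline adjustment, estimates and intervals. Dunnett rather than Tukey is a preference, and change-from-baseline contrasts within the existing ANOVA would also compare the arms directly.

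The approximations are also rough. Lognormal conversion does not fully agree with the reported p-values: the PBM-pre change at 72 h (0.180, p = 0.506) is larger than at 24 h (0.165, p = 0.285), which one common error term does not allow. The CK figures are therefore indicative only.

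Three further readings go too far:
- **NRS benefit is shown for both active arms.** This holds under equal correlation of 0.3 to 0.7. Baseline NRS is near the floor (0.6 to 1.3), so its correlation with later scores may be weaker, and the PBM-pre result then loses significance.
- **The CK effect lies in PBM-post at 72 h.** Holm p over six contrasts is 0.089, 0.046 and 0.010 at rho 0.3, 0.5 and 0.7. At 0.5 it becomes about 0.057 with nine athletes.
- **An athlete is missing.** The 271.44 mean suggests nine values, but the Results state no dropouts and the phototype counts sum to ten. It is a question to answer, not a finding.

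**Conclusion.** The omission is certain from the text, and the arm-specific conclusions outrun the reported between-arm evidence. A protective CK effect of PBM-pre is not established: the averaged ratio is near 0.76 with an interval that includes 1 at every correlation tried. Nor is it refuted, since the interval also allows roughly a halving, so a reader should not infer that PBM has no effect on CK. For NRS the direction favours both active arms, but no result should be predicted without athlete-level data. The numbers assume 10 athletes per cell, lognormal CK, normal-theory NRS and correlations that the documents do not give. The case for the change does not depend on them. This should be fixed; the omnibus tests are not invalidated.

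**What to change.** Add, labelled post hoc because results are known:
- A mixed model of log10 CK at 24, 48 and 72 h with arm, time, arm-by-time and baseline log10 CK.
- PBM-pre vs Sham and PBM-post vs Sham at each time, which localises the interaction, and averaged over 24-72 h. Give multiplicity-adjusted confidence intervals with the method and family stated (Dunnett, Holm, or 3-arm Tukey if PBM-pre vs PBM-post is also wanted).
- The same for NRS, mapDOMS, jumps and dynamometry, each with its own baseline.
- A statement of the Tukey family and error term already used, and of the number of athletes in each cell, including PBM-post CK at 72 h.

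Base the efficacy conclusions on these contrasts, and soften the protective claim for CK unless the PBM-pre vs Sham interval excludes no effect.

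The cost is SAP wording and one re-run on existing data. The result can only be reported as post hoc. CK baselines are nearly balanced, so adjustment hardly moves the CK estimates. Averaging can dilute an effect confined to one time, which is why the per-time contrasts belong beside it. With Dunnett there is no controlled comparison of the two active arms.

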## Data Analysis

Data analysis was conducted by a researcher blinded to participant group allocation. The primary outcome of the study was considered the muscle damage measured by CK levels.

The data were descriptively analyzed using mean and standard deviation. The independent variables were the experimental conditions (Sham, PBM-pre, and PBM-post) and assessment times pre, 24h, 48h, 72h after the muscle damage induction protocol. Normality and homoscedasticity assumptions were tested beforehand using the Shapiro-Wilk W Test and Levene test, respectively. The dependent variables included CK, DOMS, height of jumps in Squat Jump (SJ) and Counter Movement Jump (CMJ), and isometric manual dynamometry of the femoral quadriceps (kgf).

Two-way repeated measures analysis of variance (ANOVA) was conducted (considering pre, 24h, 48h, and 72h after the muscle damage induction protocol) followed by Tukey's post hoc test when the data showed normal distribution and variance homogeneity. In cases where the data did not present normal distribution, a logarithmic transformation (log10) was adopted, and normality and variance homogeneity were verified again for parametric tests. If the data did not meet the assumptions of normality and variance homogeneity, non-parametric tests such as Friedman's ANOVA (intragroup analyses) and Kruskal-Wallis (intergroup analyses) were employed. The significance level was set at 5%. Statistical analysis was performed using a statistical software (SPSS Statistics for Windows version 20.0, IBM, Chicago, IL, United States).

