## Study Design

[figure not shown]
The selected individuals were allocated into 3 equal groups and randomized according to the type of intervention:

- **PBM Post-Exercise Group (PBM-Post):** Submitted to the protocol of muscle damage induction and Sham photobiomodulation pre-exercise, followed by active post-exercise photobiomodulation.
- **PBM Pre-Exercise Group (PBM-Pre):** Submitted to the protocol of muscle damage induction and active pre-exercise photobiomodulation, followed by Sham post-exercise photobiomodulation.
- **PBM Sham Group (PBM-Sham):** Submitted to the protocol of muscle damage induction and Sham photobiomodulation both pre and post-exercise.

On the 1st day, all individuals were assessed using the one-repetition maximum (1RM) test to measure the loads for the muscle damage induction protocol. On the 2nd day (24 hours after the 1RM test), all groups underwent initial assessment tests (T1), which included: a) Anamnesis through a questionnaire. b) Measurement of blood levels of creatine phosphokinase (CK) using the Roche Hitachi 917 biochemical analyzer. c) Delayed onset muscle soreness (DOMS) using the numeric rating scale (NRS) and the pain location area using the pain map (mapDOMS). d) Muscle performance tests on a jump platform (Squat Jump test – SJ and Counter Movement Jump - CMJ). e) Dynamometry of the dominant knee extensor muscles with the Manual Muscle Test equipment (Lafayette Instrument).

Also on the 2nd day, the groups were irradiated with whole-body PBM (Sham or active) followed by the muscle damage induction protocol. Sequentially, participants underwent vertical jump and dynamometry tests (T2). Ten minutes after T2, participants were irradiated with active PBM or Sham according to their allocation in the groups.

Finally, on the 3rd, 4th, and 5th days, participants were reassessed (T3) for CK, DOMS, SJ/CMJ, and Dynamometry at 24h, 48h, and 72h after the muscle damage induction protocol. The study design is summarized in Figure 1.

**Figure 1.** Study Flowchart

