### ***Squat Jump (SJ)***

A repeated measures ANOVA did not reveal a moment interaction ( $F_{2,27} = 0.177$ ) and moment versus treatment interaction ( $F_{2,27} = 0.834$ ). As there was no significant interaction,

Tukey's post hoc analysis was not conducted. The means and standard deviation for SJ are presented in Table 8.

**Table 8.** Mean values ( $\pm$  standard deviation) of SJ (cm) for the Sham, PBM-pre, and PBM-post groups at pre, immediately after, 24h, 48h, and 72h after the muscle damage induction protocol:

| Groups          | SJ pre              | SJ post             | SJ 24h              | SJ 48h              | SJ 72h              |
|-----------------|---------------------|---------------------|---------------------|---------------------|---------------------|
| Sham     | 39.80 ( $\pm$ 4.60) | 39.65 ( $\pm$ 4.20) | 38.56 ( $\pm$ 4.09) | 40.10 ( $\pm$ 3.89) | 39.12 ( $\pm$ 4.13) |
| PBM-pre  | 39.96 ( $\pm$ 7.40) | 40.42 ( $\pm$ 7.54) | 38.91 ( $\pm$ 5.45) | 39.63 ( $\pm$ 6.94) | 40.32 ( $\pm$ 7.08) |
| PBM-post | 37.04 ( $\pm$ 3.74) | 38.39 ( $\pm$ 4.68) | 37.38 ( $\pm$ 5.22) | 38.18 ( $\pm$ 4.07) | 38.20 ( $\pm$ 3.77) |

**Abbreviations:** PBM (photobiomodulation); SJ (Squat Jump).

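### No sphericity check or correction is stated for the repeated-measures ANOVAs, and the NRS interaction (p = 0.044) and two NRS contrasts depend on that assumption

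*Combined protocol and SAP*

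**What the plan says.** - **Assumption checks.** Data Analysis: "Normality and homoscedasticity assumptions were tested beforehand using the Shapiro-Wilk W Test and Levene test, respectively". The SAP summary lists the same two. No section mentions sphericity, epsilon, a df correction or a multivariate test.
- **Time levels.** Data Analysis describes the two-way repeated-measures ANOVA as "considering pre, 24h, 48h, and 72h after the muscle damage induction protocol", with no distinction by outcome. Study Design adds an assessment straight after the exercise: "Sequentially, participants underwent vertical jump and dynamometry tests (T2". The Table 8 caption reports squat jump "at pre, immediately after, 24h, 48h, and 72h after the muscle damage induction protocol", and Tables 9 and 10 use the same five times. Section 3.7 plans on four times that include immediately after and omit baseline; the CK measurement section gives baseline, 24, 48 and 72 h.
- **Printed results.** Every ANOVA line has the same form. The NRS line reads "a moment versus treatment interaction ( $F_{2,27} = 0.044".
- **NRS contrasts.** One of the two contrasts at p = 0.027 is "PBM-pre group ( $p = 0.027$ ) at the moment 24h after"; the other is the Sham change from pre to 72 h.
- **Abstract.** The Sham group "reported significant increases ( $p < 0.05$ ) from 24–72 h, the PBM-pre group only at 24 h".

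**The concern.** With more than two time levels, the usual F tests for time and time-by-group are exact only if all differences between time points have equal variance (sphericity). Levene's test compares groups and says nothing about this. If the assumption fails, uncorrected p-values are generally too small. A Tukey test on one pooled within-subject error then uses the wrong standard error for individual contrasts, in either direction.

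At stake are an NRS interaction that only just passes 5% and the abstract sentence on when soreness rose in each group. The labels add to the difficulty: a reader given F2,27 and a p-value cannot tell which test was run or whether it was corrected.

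**Working it through.** **Inputs.** Ten per group, N = 30; means and SDs in Tables 6 and 8 to 10; printed p-values. Epsilon and the correlations between times are not given, so ranges are shown.

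**1. Label.** With m time levels, uncorrected df are (m−1, 27(m−1)) for time and (2(m−1), 27(m−1)) for the interaction: (3, 81) and (6, 81) for four levels, (4, 108) and (8, 108) for five. (2, 27) belongs to the group main effect, or to an interaction under the lower-bound correction. The numbers after F2,27 must be p-values, since <0.001 is called significant and 0.834 is not.

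**2. Reproducing the NRS interaction (Table 6).** Group means are 3.425, 2.375 and 2.200; time means 1.033, 4.167, 3.133 and 2.333; grand mean 2.667.
- SS = 10 × Σ(cell − group − time + grand)² = 36.15; MS = 36.15/6 = 6.025.
- p = 0.044 on (6, 81) means F = 2.279, so MSE = 6.025/2.279 = 2.644.
- The same F on (2, 27) would give p = 0.12.
- If 0.044 were itself a lower-bound p, the MSE would be 1.714. The 2.6-point contrasts would then have p = 0.0016, not the printed 0.027.

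**3. Reproducing the Tukey tests.** q = d/√(2.644/10), 12 cells, 81 df.

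| Contrast with pre | d | Predicted p | Printed p |
|---|---|---|---|
| Sham 72 h | 2.60 | 0.027 | 0.027 |
| PBM-pre 24 h | 2.60 | 0.027 | 0.027 |
| PBM-post 24 h | 1.70 | 0.459 | 0.460 |
| PBM-pre 48 h | 1.60 | 0.554 | 0.555 |
| PBM-post 48 h | 1.10 | 0.933 | 0.933 |

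One pooled error fits both the interaction and the contrasts, so both assume sphericity.

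**4. Interaction under correction.** p for F = 2.279 on (6ε, 81ε):

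| ε | 1 | 0.95 | 0.90 | 0.75 | 0.50 | 1/3 |
|---|---|---|---|---|---|---|
| p | 0.044 | 0.047 | 0.051 | 0.064 | 0.094 | 0.122 |

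The crossing is at ε ≈ 0.91 (0.907 to 0.921, allowing for rounding of 0.044). The NRS time effect (F = 52.47/2.644 = 19.8) stays below 0.001 at every ε.

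**5. The 2.6-point contrasts.** Replace the MSE by h, half the variance of the difference.
- Tukey, 12 cells, 81 df: critical q = 4.760, so p > 0.05 when h > 10 × (2.6/4.760)² = 2.98, which is 13% above 2.64.
- Bonferroni over the nine pre-versus-later contrasts: h limit = 10 × 2.6²/(2t²). With t = 2.849 (81 df) it is 4.16; with t = 3.014 (27 df) it is 3.72.

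Two covariance patterns illustrate this. Both use the pooled SDs (1.70, 2.29, 1.95, 2.16) and match MSE 2.64; they are examples, not bounds.

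| | Equal correlation 0.37 | AR(1) 0.51 |
|---|---|---|
| ε | 0.97 | 0.86 |
| Interaction p | 0.046 | 0.054 |
| Sham 72 h, Tukey, 81 df | 0.017 | about 0.08 |
| PBM-pre 24 h, Tukey, 81 df | 0.026 | 0.007 |
| Sham 72 h, Bonferroni, 27 df | 0.008 | 0.031 |
| PBM-pre 24 h, Bonferroni, 27 df | 0.012 | 0.004 |

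In both patterns Sham 24 h and 48 h stay at or below about 0.001, and no non-significant NRS contrast becomes significant.

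**6. Other tests.**
- Dynamometry time: p = 0.034 on (4, 108) means F = 2.71; p exceeds 0.05 below ε ≈ 0.76.
- CK interaction: p < 0.001 on (6, 81) needs F of at least 4.20, and 4.20 on (2, 27) gives p = 0.026. The CK and mapDOMS error terms (log10 scale) cannot be recovered from raw means.

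**7. Time levels.** MSE implied by the printed time p against that implied by the interaction p; the two should agree.

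| | Five levels | Pre, 24, 48, 72 h | Immediately after, 24, 48, 72 h |
|---|---|---|---|
| Dynamometry | 36.4 vs 36.6 | 43.3 vs 27.2 | 19.3 vs 43.2 |
| SJ | 4.11 vs 4.10 | 3.79 vs 5.84 | 5.15 vs 2.90 |
| CMJ | 3.98 vs 3.97 | 4.09 vs 4.33 | 4.00 vs 3.84 |

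SJ and dynamometry fit five uncorrected levels; CMJ discriminates weakly.

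**The case against.** The strongest reply is that this shows an omission, not an error. Epsilon cannot be estimated from the documents, a sphericity test may have been run and not reported, and the two illustrative patterns put the interaction on either side of 0.05. That stands: a reader might infer that sphericity failed and the NRS interaction is false, but nothing in the documents shows it.

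Second, the effect on the abstract depends on the multiplicity family. With nine Bonferroni contrasts, both 2.6-point contrasts stay significant in both patterns. This also stands. However, Tukey is the planned procedure, and its 12-cell form reproduces the printed p-values, so the sensitivity within that family is real.

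Third, the results already report no between-group difference at any time for NRS or CK, so sphericity does not decide whether the treatments differ at a given time. True; what it affects is the claim about time course and one abstract sentence on a secondary outcome.

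Fourth, a reader might take the labels to mean that no F test can be checked. That goes too far: the NRS F was recovered above, and the SJ and dynamometry figures are internally consistent. The accurate statement is that F statistics and correct df are not reported.

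**Conclusion.** The point holds as a gap in planning and reporting with one fragile result. The NRS interaction and within-group tests were uncorrected and used a pooled error of about 2.64. The interaction is lost if ε is below about 0.91. The Sham 72 h and PBM-pre 24 h contrasts are lost within the Tukey family if h exceeds about 2.98, and are less sensitive under the nine-contrast Bonferroni. The dynamometry time effect is lost below ε ≈ 0.76, but its post hoc tests are already null. This rests on ten per NRS cell and on the printed means and p-values.

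Two wider readings are not supported. The primary CK interaction is not overturned: if p < 0.001 holds, its lower-bound p is at most 0.026. Nor is the four-level statement wrong throughout: it is right for CK, NRS and mapDOMS, and fails only for SJ, CMJ and dynamometry, where it changes no claim. Section 3.7 counts a time at which CK is not measured; both sets have four levels, so this alone does not change N.

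**What to change.** - Fix one rule for all outcomes before the rerun: Greenhouse-Geisser. Choosing among corrections once p is known to lie near 0.05 would invite selection.
- For every time and time-by-group test, report F, both df from the output, epsilon and the corrected p, in place of F2,27.
- Recompute the within-group NRS contrasts with contrast-specific errors. Keep the planned Tukey family and show the nine-contrast Bonferroni result as a sensitivity analysis.
- If the corrected NRS interaction exceeds 0.05, do not claim that the NRS time course differs between groups. If the Sham 72 h or PBM-pre 24 h contrast exceeds 0.05, reword the matching abstract sentence.
- In Data Analysis, state the time levels per outcome. Leave the inputs in section 3.7 as recorded, and add a note that CK was analysed at pre, 24, 48 and 72 h.

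Cost: a rerun of existing data and some rewording, with no new data. Some p-values may become slightly less favourable.
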